8.3.8 ECG

Schedule and Parameters

ECG assessments will be made at screening. The parameters to be collected are: the result of sinus rhythm test, PR Interval, QRS, QT Interval, Ventricular Rate and QTc Interval.

Table presentation

For each parameter, descriptive statistics will be provided by cohort.

ECG results will also be recorded as: Normal, Abnormal Not Clinically Significant and Abnormal Clinically Significant. Summary table presenting number and percentage of subjects in each category will be provided. For percentage calculations, the total number of subjects with in each cohort in the safety population will be used as denominators. Number of subjects with missing values will be presented as a separate category.

Subject Listings

Detailed information of every measurement will be listed, by (in the order of) cohort, investigator site and subject.

8.3.9 Physical Exam

Full physical examination, including assessments of 11 body systems and Tanner stage of pubertal development, will be performed at screening. Abbreviated physical examination will be performed at visits 2, 6, 9, 12, 15, 16 in the titration periods, visits 19, 22, 25, 28 and 29 in the extension period, as well as the early termination visits in both periods. During abbreviated physical examination, the investigator will check if there any clinically significant changes from the previous evaluation

Detailed information of every measurement will be listed, by (in the order of) cohort, investigator site, subject and visit.

8.3.10 Anti-insulin antibody

Schedule and Parameters

Anti-insulin antibody will be measured at screening visit and at end of treatment visit/early termination visits in both study periods.

Table presentation

Results of anti-insulin antibody measurements will be presented in three categories: 'Positive', 'Negative' and 'Not Done' (ND). Shift table presenting change from baseline to each post-baseline analysis visit in the above categories will be provided. At each post-baseline visit, only subjects who attend both the baseline visit and the post-baseline visit will be included in the summary.

Subject Listings

Detailed information of every measurement will be listed, by (in the order of) cohort, investigator site, subject and visit.

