7.2 INCLUSION CRITERIA

Eligible subjects must meet all the following inclusion criteria for Part 1 of the study:

1. Written or oral assent from the pediatric subject and written informed consent from the parent(s) or legal guardian and a witness, as required by both state and federal laws and the local Institutional Review Board;
2. Children aged ≥ 4 and ≤ 17 years (enrolled into 3 age cohorts: 13 to 17, 8 to 12, and 4 to 7 years);
3. Clinical diagnosis of T1DM and using insulin for at least 1 year;
4. Currently receiving a regimen of basal/bolus insulin administered by MDI for at least 6 weeks prior to enrollment.
5. Subjects with pre-breakfast SMBG values between 80 and 250 mg/dL for 5 of 7 documented daily readings obtained in the week prior to Visit 2 (reading to be taken using glucometer provided at Screening Visit 1) and reported via the e-Diary;
6. Subjects on a regimen of insulin via continuous SC insulin infusion may be enrolled if they satisfy all other enrollment criteria and are willing to convert to MDI for the duration of the study, beginning 6 weeks prior to enrollment. They must continue to meet all enrollment criteria after converting to the MDI regimen;
7. Total daily insulin dose ≤ 1.5 units/kg/day with a minimum of 3 units of RAA at every meal.
8. HbA1c 7.0% to 10.0% at the time of screening;
9. Fasting serum C-peptide ≤ 0.3 ng/mL;
10. Forced expiratory volume in 1 second (FEV₁) $\geq 70\%$ of National Health and Nutrition Examination Survey (NHANES) III predicted for children ≥ 8 years of age or Wang predicted for children < 8 years of age (8), (9);
11. Forced vital capacity $\geq 70\%$ of NHANES III predicted for children ≥ 8 years of age or Wang predicted for children < 8 years of age (8), (9);
12. Subjects of childbearing potential must use “highly effective” methods of contraception. These include, for example, a state after surgical sterilization, hormonal intrauterine devices (coil), oral hormonal contraceptives, sexual abstinence or a surgically sterilized partner.

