9.1.2 Number of PK samples

The number of samples per subject and by study is indicated in [Table 3](#).

Table 3 Number of serum samples

	AFREZZA® insulin	FDKP	Anti-insulin antibody
By subject	14	5	2 ^a
Total for study (n subjects)	$14 \times 46 = 644$	$5 \times 46 = 230$	$2 \times 46 = 92$

a. Anti-insulin antibody samples to be collected at screening and end of treatment/early termination.

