9.1.3 Sample handling procedure

The sample handling procedure is summarized in [Table 4](#).

Special procedures for collection, storage, and shipment will be provided in the CLS.

Table 4 Summary of handling procedures

	AFREZZA® Insulin	FDKP	Anti-insulin antibody
Blood sample volume	2 mL	2 mL	2 mL
Serum aliquot split	1 aliquot	1 aliquot	1 aliquot
Serum storage conditions	-70°C	-70°C	-20°C
Serum shipment conditions	Dry ice	Dry ice	Dry ice

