4.2 Safety Endpoints

- Adverse events, serious adverse events, treatment-emergent adverse events
- Adverse Events of Special Interest (AESI), which include the following events:
 - Acute bronchospasm
 - Verified Clinically relevant decline in pulmonary function
 - Hypersensitivity reactions, including anaphylaxis, which can occur with insulin products, including AFREZZA[®]
 - Diabetic ketoacidosis
- Vital sign measurements

Version Date: 17-Jan-2020

- Abnormal clinical laboratory assessments
- Hypoglycemia: asymptomatic, symptomatic, nocturnal, and severe hypoglycemia according to the 2014 International Society for Pediatric and Adolescent Diabetes guideline (3)
- Anti-insulin antibodies

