Table 14.3.1.4	Treatment-emergent Adverse Events by Severity and System Organ Class/Preferred Term – Safety Population	
Table 14.3.1.5	Most Common Treatment-emergent Adverse Events Where Preferred Term Is $\geq 5\%$ – Safety Population	
Table 14.3.1.6	Treatment-emergent Serious Adverse Events by System Organ Class and Preferred Term – Safety Population	X
Table 14.3.1.7	Treatment-emergent Serious Adverse Events by Relationship to Study Drug and System Organ Class/Preferred Term – Safety Population	
Table 14.3.1.8	Treatment-emergent Adverse Events Leading to Study Discontinuation by System Organ Class and Preferred Term – Safety Population	
Table 14.3.1.9	Treatment-emergent Adverse Events Leading to Death by System Organ Class and Preferred Term – Safety Population	
Table 14.3.1.10	Treatment-emergent Adverse Events Leading to Temporary Treatment Interruption by	

	System Organ Class and Preferred Term – Safety Population	
Table 14.3.1.11	Treatment-emergent Adverse Events of Special Interest by System Organ Class/Preferred Term – Safety Population	
Table 14.3.1.12	Treatment-emergent Adverse Events of Special Interest by Relationship to Study Drug and System Organ Class/Preferred Term – Safety Population	
Table 14.3.2.1	Summary of Hypoglycemic Events – Safety Population	X
Table 14.3.2.2	Summary of Causality of Hypoglycemic Events – Safety Population	
Table 14.3.3.1	Value and Change from Baseline in Vital Signs – Safety Population	X
Table 14.3.4.1	Value and Change from Baseline in FEV ₁ – Safety Population	X
Table 14.3.4.2	Summary of Clinically Relevant Decline from Baseline in Pulmonary Function – Safety Population	X
Table 14.3.4.3	Summary of Duration of Verified Clinically Relevant Decline from Baseline in Pulmonary Function– Safety Population	
Table 14.3.5.1	Shift Table for Anti-insulin Antibody – Safety Population	X
Other		
Table 14.4.1.1	Value and Change from Baseline in HbA1c (%) – Safety Population	
Table 14.4.2.1	Average of Value and Change from Baseline in Fasting pre-breakfast SMBG (mg/dL) (eDiary Data) – Safety Population	
Table 14.4.3.1	Average of Value and Change from Baseline in Post-prandial SMBG (mg/dL) by Meal (eDiary Data) – Safety Population	
Table 14.4.4.1	Summary of 7-Point SMBG (mg/dL) by Time Point and Visit (eDiary Data) – Safety Population	
Table 14.4.4.2	Value and Change from Baseline in Mean of 7-Point SMBG (mg/dL) (eDiary Data) – Safety Population	

List of Listings		Include in DMC
Patient Disposition		

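### The only planned summary of anti-insulin antibodies is a Positive/Negative/Not Done shift table, so a rise in a child already positive at screening is tabulated as no change

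*SAP*

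**What the plan says.** SAP Section 4.2 lists "Anti-insulin antibodies" among the safety endpoints. Section 8.3.10 sets out the analysis: "Results of anti-insulin antibody measurements will be presented in three categories", namely Positive, Negative and Not Done. It continues: "Shift table presenting change from baseline to each post-baseline analysis visit in the above categories will be provided". Each row of the comparison is limited to children seen at both baseline and the later visit.

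Appendix 3 names one antibody table, 14.3.5.1, "Shift Table for Anti-insulin Antibody – Safety Population". It is marked for the DMC package. No antibody figure is listed. Section 8.3.10 also promises a subject listing: "Detailed information of every measurement will be listed". This is Listing 16.2.8.4, which is marked for the DMC as well.

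SAP Table 2 (Section 8.1.1.2) gives the antibody endpoint a screening visit, a Week 4 visit and, for children in the SAP's optional extension, a Month 12 visit. Early Termination is summarised as a visit of its own.

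On entry, Protocol Section 7.2 requires "Clinical diagnosis of T1DM and using insulin for at least 1 year".

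On the sample itself, Protocol Table 3 (Section 9.1.2) is titled "Number of serum samples" and has an antibody column. Table 4 (Section 9.1.3) has a row for "Serum storage conditions" that also covers the antibody sample. Table 5 (Section 9.1.4) gives plasma as the antibody assay matrix, with an assay volume of 250 µL.

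**The concern.** A shift table of two result categories records a change only when a child crosses the positivity cut-off. A child below the cut-off at screening can move up. A child above it can stay or move down, and any increase, however large, falls in the same cell as no increase.

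All participants come to the study with at least a year of insulin use, so positivity at screening is a foreseeable state, and the SAP's own table provides a row for it. If a fair share of children start in that row, the summary that goes into the report and to the DMC could show little movement while levels rise. A reader would have no summary statistic that says otherwise.

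The serum/plasma difference is a separate protocol matter. The tables that count and handle the sample name a different matrix from the table that describes its assay.

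**Working it through.** **The plan's own figure.** Protocol Table 3 gives 2 antibody samples per child for 46 children: 2 × 46 = 92. This reproduces. It is the only number the documents attach to this endpoint; there is no sample size, alpha or margin for it, and the analysis is descriptive (SAP Section 8.1). Under the SAP schedule the count could reach 3 × 46 = 138 if every child entered the extension.

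**Inputs.** Planned N is 46, made up of 18 + 14 + 14 (Protocol Section 7.1). The share positive at screening, *p*, is in neither document and is treated as an assumption over a wide range.

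**What the table can show.** Children who can show a negative-to-positive shift = N × (1 − *p*).

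| Assumed *p* | All 46 | Cohort of 18 | Cohort of 14 |
|---|---|---|---|
| 10% | 41.4 | 16.2 | 12.6 |
| 50% | 23.0 | 9.0 | 7.0 |
| 75% | 11.5 | 4.5 | 3.5 |
| 95% | 2.3 | 0.9 | 0.7 |

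The remaining N × *p* children start as Positive, and the table says nothing about an increase in them.

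**Illustration of what is lost.** Assume that 20% of all children have a real rise whatever their baseline status, and that every rise in a baseline-negative child crosses the cut-off. Neither assumption comes from the documents. Then 46 × 0.20 = 9.2 children have a rise, and the shift table shows 9.2 × (1 − *p*): 8.3 at 10%, 4.6 at 50%, 2.3 at 75% and 0.5 at 95%.

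**How the SAP treats other continuous measures.** FEV₁ (Section 8.3.5), HbA1c (8.3.6) and vital signs (8.3.7) are each summarised as value and change from baseline. The antibody endpoint is not.

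**Whether a level exists to summarise.** Protocol Section 9.1 names a radioimmunoprecipitation assay. Table 5 gives its quantification limit as NA, and SAP Appendix 1 has no antibody unit. Neither document defines the positivity cut-off or says whether the laboratory reports a number, a graded result or only a call.

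**Matrix, side by side.**

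| Protocol table | Matrix for the antibody sample |
|---|---|
| Table 3, sample counts | Serum |
| Table 4, handling | Serum: one aliquot, stored at −20°C |
| Table 5, assay | Plasma, 250 µL |

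Table 5 names serum for insulin and FDKP, so it distinguishes the analytes on purpose.

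**The case against.** The strongest reply is that the shift table is not the only output. Every measurement is listed by child, the DMC receives that listing, and Protocol Section 13.8 bases the safety evaluation on review of individual values as well as on descriptive statistics. With about 46 children and two or three samples each, reading the listing is feasible. This stands. A reader might infer that a rise in a baseline-positive child cannot appear anywhere in the planned output; the documents do not support that. They also do not show that the listing holds a level, since its shell is in a separate file (SAP Appendix 4). And even if levels are listed, no rule says what counts as an increase.

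Four other stronger readings are tempting and go too far:

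- *That most children will be positive at screening, so the table is nearly empty of information.* A year of insulin use makes positivity plausible but gives no rate. At 10% positive, about 41 of 46 children could still show a shift, and the table would serve well.
- *That the level is already reported and merely discarded.* The NA quantification limit and the missing unit leave this open.
- *That losing the level removes a check on outlying PK results through the insulin radioimmunoassay.* Neither document plans such a check, and the PK methods sit in a separate PK analysis plan.
- *That the matrix conflict puts the whole endpoint in doubt.* Sample collection and handling are referred to the Central Lab Specifications (Protocol Sections 9 and 9.1.3), and Table 5 is offered only as an outline. What is shown is an inconsistency within the protocol.

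It is also fair to say that a single-arm, uncontrolled study cannot attribute a rise to inhaled insulin. That limits interpretation. It does not remove the reason for describing the endpoint.

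**Conclusion.** The concern holds for the summary table. As written, the SAP has no summary of antibody level or change in level, and no category for a rise in a child positive at screening. Such a rise is tabulated as no change in Table 14.3.5.1, the only planned summary of a listed safety endpoint. This follows from the construction of the table and needs no outside fact.

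The size of the loss is not known. It runs from small (about 5 of 46 children uninformative on an increase at 10% positive: 46 − 41.4 = 4.6) to nearly complete (about 44 of 46 at 95%: 46 − 2.3 = 43.7). These figures rest on an assumed baseline positivity. Whether a better summary can be made depends on what the assay reports, which the documents leave unstated.

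The serum/plasma conflict between protocol Tables 3 and 4 and Table 5 is real but secondary.

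**What to change.** In SAP Section 8.3.10:

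1. State what the assay reports (quantitative, semi-quantitative or a call only) and how positivity is defined.
2. Where a quantitative or semi-quantitative result exists, add a table by cohort of value and change, or fold change, from screening to Week 4, Early Termination and, for children in the extension, Month 12.
3. Count treatment-emergent response as newly positive children plus baseline-positive children whose increase exceeds the assay's reproducibility limit.
4. Put this table in the DMC package beside Table 14.3.5.1, and keep the shift table.
5. If only a positive/negative call exists, state that boosting in baseline-positive children cannot be assessed.

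Separately, in the protocol, reconcile Tables 3, 4 and 5 so that they name the one matrix in which the antibody assay was validated.

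The cost is a few sentences in the SAP, one added table if levels exist, and a correction to the protocol tables. No extra sampling is needed. The downside is that the laboratory must transfer the numeric result as well as the call.

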8.4 Other Endpoints

Unless otherwise specified, safety population will be used in all the following analyses.

8.4.1 Demographics and Baseline Characteristics

Demographic characteristics including gender, race, ethnicity and date of birth will be collected at screening visit. Age (at the time of signed informed consent) will be derived using date of birth and informed consent signed date. Descriptive statistics will be provided by cohort for the above along with screening assessments including height, weight, BMI, Tanner stage, duration of T1DM and fasting serum C-peptide at screening.

The above summaries will be conducted for Safety and PK populations. For percentage calculations, the total number of subjects in each cohort in the analysis population will be used as denominators.

All the demographics and baseline disease data will also be listed, by (in the order of) cohort, investigator site and subject.

8.4.2 Extent of Study Drug Exposure

Detailed dosing information of AFREZZA[®] will be collected from the first dose to the last dose through the trial. Information of doses given during the PK Visit is captured on the eCRF, while other dosing information is captured on the eDiary.

Table Presentation

Dosing information at the PK Visit will be summarized by cohort, and presented in a subject-level listing.

For total exposure time, both numerical and categorical summaries will be provided by cohort and study period. For AFREZZA[®] doses collected on the eDiary, the following will be derived and summarized by cohort. For Cohort 1 and Cohort 2, additional summaries will be provided by starting dose, as appropriate.

- Average total daily dose of AFREZZA[®] at weekly intervals for the titration period, and at monthly intervals for the extension period. For each time interval, only data collected in the 2nd half of the interval (i.e., within 3 days prior to the each clinic visit in the titration period and within 2 weeks prior to each visit in the extension period) will be included in the summary. If a visit is performed, the actual visit date will be used to determine the time frame; if a visit is not performed, the target visit date will be used to determine the time frame. Average total daily dose is defined as the average of all total daily doses taken within a time frame. For each time interval, average total daily dose will be calculated for each subject first, and then summarized by cohort.
- Average prandial dose of AFREZZA[®] by meal at weekly intervals for the titration period, and at monthly intervals for the extension period, calculated using the same method as described above

Moreover, the use of post-meal (i.e., supplemental) doses will be presented in a summary table, by cohort and study period. Both subject-level summary (number and percentage of subjects

taking at least one post-meal dose) and dose-level summary (e.g., number of post-meal doses indicated, number of doses given, etc.) will be provided.

Graphic Presentation

Average total daily dose of AFREZZA[®] and average prandial dose of AFREZZA[®] by meal will be plotted over time to illustrate dose change throughout the study.

8.4.3 Concomitant Medications

Concomitant medications are defined as those that are started prior to first study medication dose and ongoing after, or those that started after first study medication dose. Summary table presenting number and percentage of subjects for each concomitant medication taken will be provided by cohort for the entire study. For percentage calculation, number of subjects in each cohort in the safety population will be used as denominator. In addition, detailed medication information will be listed.

Prior medications are defined as those that are stopped prior to first study medication dose, and will be presented in the same manner as concomitant medications.

Prior and concomitant medications will be coded using the WHO Drug Dictionary (version 2017 Q3). Medications will be summarized by ATC level 4 category and preferred term. Medications which cannot be coded will be summarized in a category named 'Not Codable'.

8.4.4 Medical history

Medical history information will be collected at the screening visit. A summary table will show the number and percentage of subjects with a medical history in each body system based on the safety population. The information will also be listed, by (in the order of) cohort, investigator site, and subject.

8.4.5 Fasting pre-breakfast SMBG and post-prandial SMBG

Schedule and Parameters

Fasting pre-breakfast SMBG and post-prandial SMBG at each meal will be measured daily throughout the study.

Table presentation

For each of the four parameters (fasting pre-breakfast SMBG and post-prandial SMBG at breakfast, lunch and dinner), average will be calculated at weekly intervals for the titration period and at monthly intervals for the extension period for each subject, and summarized by cohort. Same as for total daily dose and prandial dose, only data collected in the 2nd half of each interval (i.e., within 3 days prior to the each clinic visit in the titration period and within 2 weeks prior to each visit in the extension period) will be included in the analysis.

Baseline is defined as the average of all values collected prior to Visit 2. Change from baseline for a post-baseline time interval will be calculated as average of SMBG in the post-baseline time interval – baseline for each subject, and then summarized by cohort.

Graphical Presentation

For each of the four parameters, a Mean (SE) plot will be provided, presenting weekly average in the titration period and monthly average in the extension period (along with standard error) by cohort.

8.4.6 7-point SMBG

Schedule and Parameters

7-point SMBG (pre-meal and 120-150 minutes post-dose at breakfast, lunch and dinner as well as at bedtime) will be collected at screening visit, visits 6, 9, 12, 15 in the titration period, and visits 19, 22, 25, 28 in the extension period.

Table presentation

For each of the 7 parameters (pre-meal and 120-150 minutes post-dose 7-point SMBG at breakfast, lunch and dinner as well as at bedtime), average will be calculated at weekly intervals for the titration period and at monthly intervals for the extension period for each subject, and summarized by cohort. For each of these intervals, all data collected from the date of the previous on-site visit (including) to 1 day before the current visit for each visit are included in the summary.

Baseline is defined as the average of all values collected prior to Visit 2. Change from baseline for a post-baseline time interval will be calculated as average of 7-point SMBG in the post-baseline time interval – baseline for each subject, and then summarized by cohort.

Subject Listings

Detailed information of every measurement will be listed, by (in the order of) cohort, investigator site, subject and visit.

Graphical Presentation

For each of 7 parameters, a Mean (SE) plot will be provided, presenting weekly average in the titration period and monthly average in the extension period (along with standard error) by cohort.

